11.4.4 Interim analyses

Two interim analyses after 40 and 80 patients are planned according to the Pocock adjusted levels $\alpha_p = 0.0221$. Based on the results of an interim analysis the sample size can be adjusted (Lehmacher, Wassmer, 1999). There are no prespecified futility margins, but the DSMB can recommend stopping the study in the case of insufficient interim results.

11.4.5 Safety analysis

The assessment of safety will be based mainly on the frequency of adverse events (AEs) that are treatment-emergent (TEAEs). Formal tests will not be conducted for differences in safety parameters between treatment groups.

The incidence of all treatment-emergent AEs will be tabulated after grouping by system organ class and preferred term. For each preferred term and summarized over each system organ class overall, the

table will present the absolute number and proportion (%) of patients in each treatment group in whom the event occurred. The incidence of all suspected-IMP-related AEs will be tabulated similarly. The incidence of all treatment-emergent AEs will also be tabulated by severity categories.

Safety will also be summarized with respect to vital signs as mean levels by visit and change from baseline. Abnormal observations on physical exams will be listed.

11.4.6 Deviation(s) from the original statistical plan

Deviations from the planned analyses will be discussed by the Sponsor-Investigator and the biostatistician and consequently justified and reported in the final reports and the publications.

11.5 Handling of missing data and drop-outs

Withdrawn/discontinued participants will not be replaced.

Missing data for the primary variable will be imputed by means of the Last-observation-carried forward (LOCF) method.

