9. STUDY ASSESSMENTS

9.1 Study flow chart(s) / table of study procedures and assessments

Study Periods	Screening	Intervention Period				Follow-up	
		1	2	3	4	5	6
Visit	1	2	3	4	5	6	7
Time (weeks or days, or hours)	d-1 to d0 ¹	d0	d1	d2	d3-13 during admission*	d14 (+/-2d) or discharge	wk4 (+/-5d)
In- /Exclusion Criteria	x						
Patient Information and Informed Consent	x						
Randomisation	x						
Demographics		x					
Medical History and Physical Examination		x				x	
Vital Signs including Respiratory Rate ⁹		x	x	x	x	x	
Laboratory Tests (blood)		x	x		x ³	x	
Virology testing		x ²			x ²	x ²	
Administer Study Medication ⁴		x	x	x	x		
Assessment of WHO ordinal scale		x	x	x	x	x	x
Assessment of ICU admission and/or mechanical ventilation		x	x	x	x	x	x
Laboratory assessment in detail:							
Routine full blood count		x ⁵	x		x ³	x	
Routine coagulation studies		x ⁵	x		x ³	x	
Routine biochemistry including LDH		x ⁵	x		x ³	x	
Serum pregnancy test	x ⁶						
Ferritin, IL-6, D-Dimer		x ⁵	x ¹¹		x ³	x	
C1INH concentration ⁷		x	x			x	
Additional samples in Basel ¹⁰ :		x					
Complement proteins (e.g. C4d, C5a)		x	x		x ³	x	
Inflammatory cytokines (e.g. IL-10)		x	x		x ³	x	
Contact activation and coagulation proteins (e.g. factor XII)		x	x		x ³		
C1INH concentration and activity		x ⁸	x ⁸		x (d3, 7, 10)	x	
Urinary markers of renal injury		x	x		x ³	x	
Blood volume (ml), total/study specific (Basel ¹⁰)	5/5 (5)	12/12 (22)	12/12 (22)		12/5 (10)	12/12 (17)	
Urine volume (ml), study specific in Basel ¹⁰		5	5		5	5	
(Serious) Adverse Events		x	x	x	x	x	x

¹Eligibility criteria have to be assessed within 72 hours after hospital admission. Randomisation may occur on the day of hospital admission.

²Monitoring of SARS-CoV-2 viral load will be performed in Basel and optional in other centers. This will include performance of a quantitative SARS-CoV-2 PCR from upper or lower respiratory tract at baseline

and subsequently once between day 4-7 (according to local standard) and again on day 14 if participants are still admitted or between day 10-13 if discharged earlier. Standard operating procedures include the performance of a second swab following a first negative swab.

³Routine laboratory tests will be performed on days 3, 5, 7, and 10 during hospital admission according to standard procedures of the study site, but will include a set of hematology, coagulation and biochemistry parameters. Additional blood samples will be collected at the same time.

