⁴IMP will be administered during a 64 hour period (+/-4 hours). Trial medication will be stopped in participants that are discharged or transferred to another facility.

⁵Can be omitted if results are available from the same day.

⁶A pregnancy test will be performed in women who may become pregnant, are sexually active, and do not use adequate contraceptive measures.

⁷Collection of samples will be before 1st administration of study medication and subsequently at least 4 hours after the administration of study medication.

⁸Collection of samples will be before 1st administration, 10 (+/-5) minutes after the 1st administration (day 0) and before and 10 (+/-5) minutes after one administration on day 1.

⁹The worst value recorded on a given day will be documented.

¹⁰optional for other centers depending on their ability to collect, centrifuge, aliquot and store blood and urine samples at -80°C.

¹¹IL-6 will not be measured on day 1

* If the patient was already discharged before day 7, the assessment of the WHO ordinal scale will be conducted via a short telephone interview (Score 1 or 2).

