9.2 Assessments of outcomes

9.2.1 Assessment of primary outcome

For the analysis of the primary endpoint, illness severity will be assessed on each day after enrolment (worst status) with the use of the WHO Ordinal Scale for Clinical Improvement (score 0 will be omitted and score 6 and 7 will be combined) and the score on day 7 will be analysed stratified by its baseline value.

Patient State	Descriptor	Score
Uninfected	No clinical or virological evidence of infection	0
Ambulatory	No limitation of activities	1
	Limitation of activities	2
Hospitalized Mild disease	Hospitalized, no oxygen therapy	3
	Oxygen by mask or nasal prongs	4
Hospitalized Severe Disease	Non-invasive ventilation or high-flow oxygen	5
	Intubation and mechanical ventilation	6
	Ventilation + additional organ support – pressors, RRT, ECMO	7
Dead	Death	8

Figure 4: WHO ordinal scale for clinical improvement. For the current study, score 0 will be omitted, and score 6 and 7 will be combined.

The worst score on a given day (between 0:00 and 24:00 hours) will be used for the categorization

Patient State	Description	Score
---------------	-------------	-------

Outpatient	No limitation in activities	1
	Limitation in activities	2
Hospitalized Mild disease	No oxygen therapy	3
	Oxygen by mask or nasal prongs	4
Hospitalized Severe disease	Non-invasive ventilation or high-flow oxygen	5
	Intubation, mechanical ventilation +/- additional organ support	6
Death	Death	7

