- Only in Basel and in the active treatment group: Collection of blood (5ml) for the analysis of C1INH levels and activity 10 (+/-5 minutes) after the first administration.

Visit 3, Intervention period (Day 1)

- Administration of 4200 U of conestat alfa every 8 hours in the active treatment group as per treatment schedule. The time of dosing and the dose will be recorded.
- Assessment of vital signs including respiratory rate.
- Assessment of WHO ordinal scale and need for oxygen supplementation
- Documentation of ICU admission and/or non-invasive or invasive ventilation
- Collection of blood (12ml) for analysis of ferritin, D-Dimer, C1INH concentration, and in Basel (optional for other centers): collection of blood (5ml) and urine (5ml) for the analysis of complement proteins, parameters of the contact activation and coagulation system, renal injury markers and inflammatory cytokines. Routine full blood count, coagulation and biochemistry studies will only be performed if results from prior tests on the same day are not available.
- Only in Basel and in the active treatment group: Collection of blood (5ml) for analysis of C1INH levels and activity 10 (+/-5 minutes) after any of the three administrations of conestat alfa on that day.

- Assessment of AEs.

Visit 4, Intervention period (Day 2)

- Administration of 4200 U of conestat alfa every 8 hours in the active treatment group as per treatment schedule. The time of dosing and the dose will be recorded.
- Assessment of vital signs including respiratory rate.
- Assessment of WHO ordinal scale and need for oxygen supplementation
- Documentation of ICU admission and/or non-invasive or invasive ventilation
- Assessment of AEs.

Visit 5, Intervention period (Day 3-13 during hospital admission)

- Completion of treatment with conestat alfa (9 administrations in total including the first 8400 U administration) in the active treatment group as per treatment schedule. The time of dosing and the dose will be recorded.
- Assessment of vital signs including respiratory rate.
- Assessment of WHO ordinal scale and need for oxygen supplementation. If the patient was already discharged before day 7, the assessment of the WHO ordinal scale will be conducted via a short telephone interview (Score 1 or 2).
- Documentation of ICU admission and/or non-invasive or invasive ventilation

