11.4 Planned Analyses

11.4.1 Datasets to be analysed, analysis populations

A review of the database will be conducted in a blinded manner shortly before the database will be locked, and any decisions made at that meeting (blinded Data Review Meeting) concerning the statistical analysis, e.g., additional outcomes and populations, pooling of sites for efficacy analysis, will be documented in the Statistical Analysis Plan (SAP).

Missing data for the primary endpoint will be imputed by means of the Last-observation-carried-forward (LOCF) method.

Safety Population: The Safety Population is defined as all patients who received at least one dose of conestat alfa. Statistical analyses will be based on the actual treatment the patient received.

Full Analysis Set/Intent-to-Treat Population: The FAS/ITT Population is defined as all patients who are randomly allocated to a study arm. Statistical analyses will be based on the treatment arm to which the patient was allocated.

For quantitative data, the number of patients with non-missing information, means, medians, standard

deviations and extremes will be determined. For qualitative data, absolute and relative frequencies will be calculated. Moreover, changes from baseline (V2, d0) will be calculated.

Per Protocol Population: The PP Population is defined as all patients in the FAS/ITT Population who complete the study and who do not have any major protocol violations, including the following:

- Patients who had major inclusion/exclusion criteria violations.

Sufficient compliance is expected because of IV administration of the IMP.

The PP Population will be determined by a blinded review in the Data Review Meeting (DRM) of the data prior to database lock.

The primary efficacy analysis will be based on the FAS/ITT Population in this superiority trial; an additional efficacy analysis will be performed on the PP Population. The Safety Population will be used for all safety analyses.

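### For a patient discharged before day 7 and not reached by telephone, LOCF carries an inpatient score although the patient is known to have left hospital

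*Protocol*

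**What the plan says.** The primary endpoint is the day-7 score on a 7-category scale; section 9.2.1 adds that "the score on day 7 will be analysed stratified by its baseline value". Categories 1 and 2 are outpatient states, 3 to 6 are inpatient states and 7 is death.

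- **Missing scores.** Section 11.5: "Missing data for the primary variable will be imputed by means of the Last-observation-carried forward (LOCF) method". Section 11.4.1 says the same: "Missing data for the primary endpoint will be imputed by means of the Last-observation-carried-forward (LOCF) method". No exception is given for a patient whose status is known from another source.
- **Daily score.** Section 9.2.1: "The worst score on a given day (between 0:00 and 24:00 hours) will be used for the categorization".
- **Schedule.** The Visit 5 column of the flow chart in section 9.1 is headed "d3-13 during admission".
- **After discharge.** For a patient who left before day 7, section 9.3.1 (Visit 5) says that "the assessment of the WHO ordinal scale will be conducted via a short telephone interview (Score 1 or 2"). The footnote to the flow chart agrees.
- **Other sources of status.** Section 9.2.3 collects discharge dates and four-week mortality. The week-4 contact in section 9.3.1 (Visit 7) covers the WHO scale, ICU admission and ventilation, with charts, discharge summaries and the general practitioner as back-up.

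**The concern.** Read together, these rules let the imputed value contradict a recorded fact. A patient goes home on day 5, the day-7 call is not answered, and the last score on file is that of day 5. Under the worst-of-day rule this is an inpatient category. LOCF then enters 3 or 4 as the day-7 score, although the protocol itself places a discharged patient at 1 or 2. A patient who entered at 3 and went home early would appear unchanged. Yet the time-to-improvement endpoint (section 5.2) counts the same live discharge as an improvement.

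The error is not random noise. It can occur only in patients who have gone home, so it pulls the arm with more early discharges towards the other arm. If conestat alfa speeds discharge, the error dilutes the benefit. If controls go home sooner, it dilutes that difference instead. The same scores feed the interim looks after 40 and 80 patients.

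**Working it through.** **Yardstick.** Section 11.2 gives SD 1.5, target difference 1 point, two-sided alpha 0.05, power 0.80 and 2 × 38 patients. A two-sample t-test needs 36.3 per arm. Dividing by the Wilcoxon efficiency 0.955 gives 36.3/0.955 = 38.0, which matches. With 80 + 40 patients, the standard error of a difference in means is 1.5 × √(1/80 + 1/40) = 0.29.

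**Error per patient.** True score 1 or 2, carried score 3 or 4: an error of 1 to 3 points, 2 on average (3.5 − 1.5).

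**Bias formula.** Let *s* be the error per patient, *m* the share of calls missed (taken as equal in both arms), and *h* the share discharged by day 7. The bias against conestat alfa is *s* × *m* × (*h* conestat − *h* control). The protocol gives neither *m* nor *h*, so both are assumptions.

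Example with 65% versus 40% discharged, *s* = 2, *m* = 10%:
- conestat mean overstated by 2 × 0.10 × 0.65 = 0.13
- control mean overstated by 2 × 0.10 × 0.40 = 0.08
- bias 0.13 − 0.08 = 0.05 point, about 0.05/0.29 = 0.17 standard errors

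At *m* = 20% the bias doubles to 0.10 point.

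| Discharged, conestat vs control | 5% missed | 10% missed | 20% missed |
|---|---|---|---|
| 50% vs 40% | 0.01 (0.005–0.015) | 0.02 (0.01–0.03) | 0.04 (0.02–0.06) |
| 60% vs 40% | 0.02 (0.01–0.03) | 0.04 (0.02–0.06) | 0.08 (0.04–0.12) |
| 70% vs 40% | 0.03 (0.015–0.045) | 0.06 (0.03–0.09) | 0.12 (0.06–0.18) |

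Entries are for *s* = 2; brackets are for *s* = 1 to 3.

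**Power.** For a single look at alpha 0.0221 with 80 + 40 patients and a true 1-point effect, power is 0.876 without bias, 0.845 at a bias of 0.04, 0.828 at 0.06 and 0.703 at the extreme of 0.18. This is a yardstick and not the power of the three-look design.

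**Rank-based check.** The planned test is nonparametric, so a simulation was run on assumed category distributions with 60% versus 40% at home and a true mean difference of 0.68. It used an unstratified Mann-Whitney test at alpha 0.05 with 80 versus 40 patients.

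| Unreached | Difference: LOCF | Difference: scored 2 | Power: true scores | Power: LOCF | Power: scored 2 |
|---|---|---|---|---|---|
| 10% | 0.64 | 0.67 | 0.58 | 0.53 | 0.575 |
| 20% | 0.60 | 0.66 | 0.57 | 0.48 | 0.56 |

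Scoring an unreached discharged patient as 2 recovers most of the loss.

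**Worsening patients.** In the same simulation, carrying 20% of those truly at 5 or above as 4 moved the difference from 0.68 to 0.65 and left power at 0.57.

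**The case against.** **The telephone call may not be the only source.** Section 9.2.1 calls for scoring on each day after enrolment, and section 9.2.2 for scoring every day to day 14. If scores are taken after discharge and before day 7, the carried value may already be 1 or 2. Nothing limits the number of call attempts either. This stands in part: the flow chart ties days 3–13 to admission, so the sections conflict, and the error arises under the flow-chart reading.

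**The size rests on assumed rates.** This stands. With equal discharge and contact rates in both arms, the formula gives zero bias.

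**A reader might infer that LOCF also freezes deteriorating patients at a better score and so hides harm.** The documents do not support that as a general effect. Inpatients who worsen are scored daily, and ventilation and death are assessed every day to day 14 (section 9.2.2). The transfer footnote, "Trial medication will be stopped in participants that are discharged or transferred to another facility", ends medication and not follow-up. Section 9.2.5 keeps most withdrawn patients in follow-up. What remains is consent withdrawals, patients withdrawn without having received study medication, and any transfers for whom no day-7 score is obtained. The simulated effect on power was negligible.

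**Using the week-4 contact would come too late.** Section 11.2 has the primary endpoint analysed at the latest 14 days after start of treatment, and the interim looks may fall before many week-4 contacts. This stands and limits what the fix may require.

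**A sensitivity analysis may be in the SAP.** It may be, but the primary imputation rule is fixed in the protocol.

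**Conclusion.** The point holds for patients discharged before day 7 and not reached. For them, LOCF without exception, worst-of-day scoring and inpatient-only scheduling together produce a score that contradicts known status. The bias runs against the arm with more early discharges. Assuming 65% versus 40% discharged and a 2-point error, it is about 0.05 point per 10% of calls missed, or 5% of the 1-point target. Across the assumed ranges in the table it runs from 0.005 to 0.18 point. It is small if few calls fail, and it would not by itself undermine the trial. The change is still worth making, because it is cheap and replaces a value known to be wrong. The stronger inference, that LOCF systematically conceals deterioration, is not supported.

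**What to change.** Amend sections 11.4.1 and 11.5 so that known status overrides LOCF:

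1. A patient recorded as discharged alive before day 7, with no readmission or death known at the time of the analysis, is scored 2 (sensitivity analysis: 1).
2. A known death by day 7 is scored 7. The scale already implies this; stating it prevents LOCF from being applied.
3. For readmitted or transferred patients, available hospital records are used.
4. Only scores still unknown, for example after consent withdrawal, are imputed. Use either multiple imputation from daily scores, baseline score, site and arm, or LOCF with best-case and worst-case sensitivity analyses.
5. Week-4 information may update the final analysis but must not be required for the interim looks.

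Reconcile two further pairs of sections. Section 8.5 ends follow-up at consent withdrawal, whereas 9.2.5 offers a week-4 interview. Section 9.1 schedules days 3–13 during admission, whereas 9.2.1 and 9.2.2 call for daily scoring without that limit. If scoring continues after discharge, the problem largely disappears.

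Cost: wording and a little more analysis work. Multiple imputation, if chosen, must be fitted to the stratified rank test and the inverse-normal combination. Obtaining records from outside facilities may take some effort. A single assigned value for unreached discharged patients is itself a simplification. With true scores averaging 1.5, the remaining error is 0.5 × 0.10 × 0.25 = 0.0125 point at 10% missed calls, against 0.05 under LOCF. The change should be made before interim data are seen.

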12. QUALITY ASSURANCE AND CONTROL

The Sponsor-Investigator and the local site investigators are responsible for proper training of all involved study personnel and for implementing and maintaining quality assurance and quality controls systems with written SOPs and working instructions. All SOPs and working instructions will be prepared and critically evaluated by the investigators and study nurses before commencement of the trial and by the monitoring organization.

12.1 Data handling and record keeping / archiving

12.1.1 Case Report Forms

Study data will be recorded in an electronic data capture (EDC) system via an electronic Case Report Form (eCRF) which is provided by the Clinical Trial Unit (CTU), University Hospital Basel (secuTrial®). A unique study code will be used for identification of participants in the eCRF. Subjects will not be identified on the eCRF by name or date of birth.

Only authorized personnel will be able to make eCRF entries via a personalized login to the eCRF and are responsible for entering complete data.

If source data is available as a print-out (e.g. laboratory values), this print-out will be kept on file in a source data folder, and the data necessary for the study is to be transferred to the eCRF immediately.

12.1.2 Specification of source documents

Source data include the paper and electronic records of the hospitals at the respective study sites and all study documents (AE/SAE form, informed consent forms, laboratory reports etc.). Source data includes demographic data, visit dates, informed consent forms, randomisation numbers, SAEs, AEs, concomitant medication, results of physical examination and information related to COVID-19 infection (e.g. data from viral sampling). Source data may be found either in the electronic or paper-based records of the hospitals at the respective study sites or as a print-out of study-related laboratory results which will be mailed to the local investigators from the central laboratory hospitals at the respective study sites or will be provided to the Sponsor-Investigator by the blinded technician of the Clinical Immunology Laboratory of the University Hospital Basel (only relevant for the subgroup of patients included in Basel).

12.1.3 Record keeping / archiving

All study data will be archived for a minimum of 10 years after study termination or premature termination of the clinical trial. Study data will be archived in a password protected database on a protected server at the University Hospital Basel. Blood samples for the subgroup of patients undergoing analysis of inflammatory proteins will be stored in a dedicated freezer with limited access at the Department of Biomedicine of the University Hospital Basel. Any study relevant source data and documents will be archived at each study site for a minimum of 10 years.

12.2 Data management

Study data will be captured via an online Clinical Data Management System (CDMS) secuTrial, based at the IT-department of the University Hospital Basel. The data collected is entered into the study eCRF. An audit trail will maintain a record of initial entries and any changes made; time and date of entry; and user name of person authorizing entry or change. For each patient enrolled an eCRF must be completed. The principal investigator and Co-Investigator at the study site will be responsible for assuring that the data entered into the eCRF is complete, accurate, and that the entry and updates are performed in timely manner. If a patient withdraws from the study, the reason must be noted on a dropout form of the eCRF.

12.2.1 Data Management System

The eCRF will be implemented by the Data management group at the Clinical Trial Unit (CTU) of the University Hospital Basel using the Clinical Data Management System (CDMS) secuTrial. The CDMS runs on a server maintained by the IT-department of the University Hospital Basel. Additional storage capacity can be added as needed. Data entry will be performed by trained clinical investigators.

